7.2.1.3 Adverse Events Expected Due to Study Related Endpoints

7.2.1.3.1 Deaths

For this study, mortality is an efficacy endpoint. Deaths that occur during the protocol specified adverse event reporting period (Section 7.3) that are more likely related to disease progression will therefore be an expected adverse event and will not be subject to expedited reporting.

Death should be considered an outcome and not a distinct event. The event or condition that caused or contributed to the fatal outcome should be recorded as the single medical concept on the Adverse Event eCRF. Generally, only one such event should be reported. The term "sudden death" should only be used for the occurrence of an abrupt and unexpected death due to presumed cardiac causes in a subject with or without preexisting heart disease, within 1 hour of the onset of acute symptoms or, in the case of an unwitnessed death, within 24 hours after the subject was last seen alive and stable. If the cause of death is unknown and cannot be ascertained at the time of reporting, "unexplained death" should be recorded on the Adverse Event eCRF. If the cause of death later becomes available (e.g., after autopsy), "unexplained death" should be replaced by the established cause of death.

7.2.1.3.2 Expected Adverse Events Due to Glioblastoma

Adverse Events that may be expected due to the subject's underlying glioblastoma or its standard therapy include headache, seizure, neutropenia and progression of underlying GBM, and progression of GBM leading to death, etc. These events are considered expected AEs for this study regardless of ABT-414 treatment. As such, individual subject cases of these events, when considered serious, will not be reported in expedited fashion as individual cases, but will be evaluated during aggregate reviews by the IDMC. [Appendix III](#) includes a complete list of the adverse events that will be considered as expected for reporting purposes, based on events commonly related to underlying glioblastoma or complications from glioblastoma standard therapy.

7.3 Adverse Event Severity

The Investigator will rate the severity of each adverse event according to the National Cancer Institute Common Terminology Criteria for Adverse Events (NCI CTCAE Version 4.0)²⁷

For adverse events not captured by the Common Terminology Criteria, the following should be used:

Grade 1	The adverse event is transient and easily tolerated by the subject (mild).
Grade 2	The adverse event causes the subject discomfort and interrupts the subject's usual activities (moderate).
Grade 3	The adverse event causes considerable interference with the subject's usual activities and may be incapacitating (severe).
Grade 4	Life threatening; urgent intervention.
Grade 5	The adverse event resulted in death of the subject (severe).

Relationship to Protocol Treatment

The Investigator will use the following definitions to assess the relationship of the adverse event to the use of protocol treatment, with separate assessments for each component of therapy (ABT-414/placebo, TMZ and radiation therapy):

Reasonable Possibility	After consideration of factors including timing of the event, biologic plausibility, clinical judgment, and potential alternative causes, there is sufficient evidence (information) to suggest a causal relationship.
No Reasonable Possibility	After consideration of factors including timing of the event, biologic plausibility, clinical judgment, and potential alternative causes, there is insufficient evidence (information) to suggest a causal relationship.

Reasonable possibility is defined such that the specific treatment (ABT-414/placebo, TMZ, or radiation therapy) is more likely to be the cause of the event than any other reason, whereas no reasonable possibility is defined as the Other cause of the event is more likely. For causality assessments, events assessed as having a reasonable possibility of being related to protocol treatment will be considered "associated." Events assessed as having no reasonable possibility of being related to protocol treatment will be considered "not associated." In addition, when the Investigator has not reported a causality or deemed it not assessable, AbbVie will consider the event associated.

If an Investigator's opinion of no reasonable possibility of being related to protocol treatment is given, an Other cause of event must be provided by the Investigator for the serious adverse event.

[figure not shown]
7.4 Adverse Event Collection Period

All protocol related serious adverse events and non-serious adverse events must be reported as follows:

- From time the study-specific informed consent is signed, but prior to the initial administration of component therapy, will only be collected if they are considered by the Investigator to be causally related to the study-required procedures.
- From first day of component therapy administration until 49 days after last administered dose of ABT-414.

Adverse event information will be collected as shown in [Figure 1](#).

Figure 1. Adverse Event Collection

* Only if considered by the Investigator to be causally related to study required procedures.

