An interim efficacy analysis based on a data cut of 30 April 2019 was performed by the RTOG Independent Data Monitoring Committee (IDMC), at which time 346 OS events had been observed out of 639 subjects included in the main part of the study. The primary analysis of OS based on the Intent-to-Treat (ITT) population showed no difference in OS between groups, with a median OS of 18.9 vs. 18.7 months for ABT-414 and placebo, respectively. The weighted ($\rho = 0$, $\gamma = 0.2$) stratified log-rank test p-value (1-sided) was 0.628, and the observed hazard ratio (HR) (95% CI) for OS was 1.01 (0.82, 1.25). The median PFS was 8.0 vs. 6.3 months for ABT-414 and placebo, respectively, with a stratified log-rank test p-value (1-sided) of 0.029. The observed hazard ratio (HR) (95% CI) for PFS was 0.84 (0.70, 1.02). Preliminary analysis of demographic and clinical characteristics did not reveal any factors predictive of OS benefit for the addition of ABT-414 to standard RT/TMZ therapy.

Overall, 99.4% and 97.8% of subjects experienced at least 1 adverse event, and 87.3% and 62.3% experienced a Grade 3 or higher AE in the ABT-414 and placebo arms, respectively. Overall, 94.7% and 36.1% of subjects experienced at least 1 ocular adverse event related to corneal epitheliopathy, 61.0% and 0.6% experienced a Grade 3 or higher AE related to corneal epitheliopathy, and 11.8% and 0% discontinued study drug (ABT-414 or placebo) in the

ABT-414 and placebo arms due to corneal epitheliopathy, respectively. The most common (> 10%) events related to corneal epitheliopathy included keratopathy, vision blurred, photophobia, dry eye, eye pain, keratitis, and punctate keratitis. Excluding events related to corneal epitheliopathy, events for which the incidence in the ABT-414 group was $\geq 5\%$ greater than in the placebo group included thrombocytopenia, gamma-glutamyltransferase increased, aspartate aminotransferase increased, alanine aminotransferase increased, constipation, blood alkaline phosphatase increased, fatigue, and platelet count decreased. Excluding events related to corneal epitheliopathy, Grade 3 or higher events for which the incidence in the ABT-414 group was at least 5% and was $\geq 2\%$ greater than in the placebo group included thrombocytopenia, gamma-glutamyltransferase increased, and alanine aminotransferase increased.

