- j. MRI to be performed \leq 14 days before the start of each odd-numbered cycle or follow-up visit, starting at Cycle 1. If the subject discontinues study drug prior to disease progression, MRIs should continue to be obtained approximately every 8 weeks until disease progression is confirmed.

- k. MRI to be performed, if not performed within last 3 weeks, if subject withdraws from study prior to disease progression.
- l. TMZ will be administered once daily on Days 1 through 5 of each 28-day cycle for 6 cycles per the local prescribing information.
- m. ABT-414 or placebo infusion will be administered on Day 1 and Day 15 of each 28-day cycle for 12 cycles. For subjects demonstrating continued benefit and no unacceptable toxicity with ABT-414/placebo after 12 cycles, the Adjuvant Phase may be extended at the discretion of the Investigator in discussion with the Neuro-Medical Oncology Chair or AbbVie Medical Monitor, with continued ABT-414/placebo treatment until disease progression is confirmed.
- n. Prophylactic eye drops will be administered daily for 7 days with each dose of ABT-414/placebo, from 2 days before until 4 days after each dose of study drug (ABT-414 or placebo), as described in Section 5.5.
- o. These assessments should be completed prior to study drug administration and any other study procedures being performed at these visits, and prior to discussing with the subject whether disease progression has occurred.
- p. To be assessed at the time of disease progression (as soon as possible), regardless of the study phase in which disease progression occurred, or upon study withdrawal for any other reason.
- q. Survival will be assessed quarterly after treatment discontinuation until death.
- r. If the subject is unable to return to the site for the Day 49 Follow Up Visit, a phone call may be conducted to obtain AE and concomitant medication information.

Table 3. Blood Samples for Biomarker and Pharmacokinetic Schedule of Assessments*

Chemoradiation Phase					
Activity	Day 1 Wk 1 (Fraction 1 of RT)	Day 1 of Wk 2	Day 1 of Wk 3	Day 1 of Wk 4	Day 1 of Wk 5
Plasma Markers	0 hour (pre-dose)				
Serum Markers	0 hour (pre-dose)				
PK – ABT-414 and Total ABT-806 Assays	0 hour (pre-dose) & within 30 min post-dose	Anytime from 4 days before (preferred) to 1 day after the scheduled visits	0 hour (pre-dose) & within 30 min post-dose	Anytime from 4 days before (preferred) to 1 day after the scheduled visits	0 hour (pre-dose) & within 30 min post-dose

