Subjects in Arm A will receive ABT-414 on Day 1 and Day 15 of each 28-day cycle. Subjects in Arm B will receive placebo IV infusion on Day 1 and Day 15 of each 28-day cycle. Subjects who discontinue TMZ for TMZ-related toxicity will continue ABT-414/placebo treatment. Subjects who discontinue ABT-414 or placebo due to ABT-414-related or placebo-related

toxicity prior to completion of the Adjuvant Therapy Phase will continue TMZ treatment as scheduled.

Duration of Adjuvant ABT-414 or Placebo

If after completing 12 cycles of adjuvant ABT-414/placebo, the subject is tolerating treatment and the Investigator believes the subject is continuing to benefit from ongoing study drug treatment, the Investigator may extend the Adjuvant Phase with ABT-414/placebo after consultation with the Neuro-Medical Oncology Chair or AbbVie Medical Monitor. The ABT-414/placebo will continue at the same dosing schedule, as long as disease progression has not been determined.

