5.6 Duration of Therapy

In the absence of treatment delays due to adverse event(s), treatment may continue as specified in the treatment plan overview, Section 5.1, or until one of the following criteria applies:

- Subject experiences disease progression (except as noted below)
- Subject experiences intercurrent illness that prevents further administration of treatment
- Subject experiences excessive toxicity precluding further therapy with either ABT-414 or TMZ, according to the Investigator
- Subject decides to withdraw consent for participation in the study

- General or specific changes in the subject's condition render the subject unacceptable for further treatment in the judgment of the Investigator
- Subject become pregnant while on study

Subjects unable to continue either TMZ or ABT-414/placebo due to excessive drug-specific toxicity will be allowed to continue therapy with the other, tolerated therapy components until one of the other criteria above is met.

Subjects discontinuing therapy in the absence of progression should not receive any other cancer treatment before their disease progresses, unless this is clearly not in the interest of the subject.

ABT-414 treatment may be continued at the investigator's discretion if for any reason there is uncertainty about whether true disease progression has occurred. As anecdotal cases of drug-related pseudoprogression have been reported, which were associated with both initial clinical and radiological deterioration and appeared to have a different temporal course and characteristics to traditional radiotherapy-related pseudoprogression, investigators may consider biopsy prior to study drug discontinuation. If, after treatment discontinuation, there is additional clinical information leading the investigator to conclude that the reason for discontinuation is no longer valid, the subject may resume study treatment as long as no other chemotherapy, radiotherapy, immunotherapy, NovoTTF, or other treatment with antineoplastic intent has been received, with the exception of surgical intervention that yields histology not demonstrative of tumor progression.

After progression, the treatment will be left to the discretion of the Investigator. Any anti-cancer therapy other than the study drug will not be considered as part of the protocol treatment. However, treatments will be recorded.

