7.2 Medical Complaints

The Investigator will monitor each subject for clinical and laboratory evidence of adverse events (AE) on a routine basis throughout the study. The Investigator will assess and record any adverse event in detail including the date of onset, event diagnosis (if known) or sign/symptom, severity, time course (end date, ongoing, intermittent), relationship of the adverse event to study drug, and any action(s) taken. For serious adverse events considered as having "no reasonable possibility" of being associated with study drug, the Investigator will provide an Other cause of the event. For adverse events to be considered intermittent, the events must be of similar nature and severity. Adverse events, whether in response to a query, observed by site personnel, or reported spontaneously by the subject will be recorded.

All adverse events will be followed to a satisfactory conclusion.

Adverse event reporting is required for all protocol treatment modalities: ABT-414/placebo, TMZ, and radiation therapy.

The NCI CTCAE v.4 will be used for adverse event reporting/grading of event severity.

All ophthalmology exam reports will be reviewed by the Investigator (or medically qualified delegate). With the exception of the corneal findings described below, decisions on *which* findings from ophthalmologic examinations, if any, will be reported as adverse events, as well as the *grading* of any such events, will be made according to the Investigator's judgment. These events will be graded according to NCI CTCAE v.4²⁷ criteria, and *not* according to the grading system used for the ophthalmology examinations.

To ensure consistent reporting of the corneal findings characteristic of ABT-414 that are not well described by the MedDRA preferred terms or CTCAE grading, any abnormal finding on either the "Microcysts/Edema" or "Superficial Punctate Keratopathy" field of

the ABT-414-TOE must be recorded as an adverse event of "microcystic keratopathy" with severity grading as shown in Table 5 (see Section 4.2 for additional details).

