7.3 Definition of Treatment Emergent Observation for Safety Analysis

For safety assessments, Treatment Emergent (TE) observations are defined as all newly occurring or worsening safety observation with onset at or following the initiation (date and time) of any study drug and no later than 49 days after the last dose of Depatux-M/Placebo.

If an incomplete onset date is collected for an AE, the AE will be assumed to be treatment-emergent unless there is evidence that confirms that is it not.

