11.2 Analysis of Adverse Events

11.2.1 Treatment-Emergent Adverse Events (TEAEs)

TEAEs are defined as any AE with onset or increased severity after the first dose of study drug (RT/TMZ/Depatux–M or matching placebo) and no more than 49 days after the last dose of Depatux-M/placebo. Incidence of TEAEs will be summarized in chemo-radiation phase and adjuvant phase separately and also in the overall study.

Chemo-radiation phase is defined as from the Study Rx Day 1 to the day before the first adjuvant dosing. If adjuvant dosing is missing then, last Depatux-M/Placebo dosing + 49 days would be the end date of chemo-radiation phase. Adjuvant phase is defined as day of first adjuvant dosing to the last Depatux-M/Placebo dosing + 49 days.

Adverse Event Overview

The number and percentage of subjects experiencing TEAEs between the treatment groups will be summarized for the following adverse event categories.

- Any TEAE
- Any TEAE possibly related to any study drug
- Any TEAE possibly related to Depatux-M, TMZ and RT, separately
- Any TEAE with CTCAE grade 3 or higher
- Any TEAE with CTCAE grade 4 or higher
- Any Grade 3 or higher TEAE possibly related to any study drug
- Any Grade 3 or higher TEAE possibly related to Depatux-M, TMZ and RT, separately
- Any Grade 4 or higher TEAE possibly related to any study drug
- Any Grade 4 or higher TEAE possibly related to Depatux-M, TMZ and RT, separately
- Any TE serious AE (SAE)
- Any TE SAE possibly related to any study drug
- Any TE SAE possibly related to Depatux-M, TMZ and RT, separately
- Any TEAE leading to discontinuation of Depatux-M or Placebo, TMZ and RT, separately
- Any TEAE leading to discontinuation of Depatux-M possibly related to any study drug
- Any TEAE leading to discontinuation of Depatux-M/Placebo, possibly related to Depatux-M
- Any TEAE leading to discontinuation of TMZ, possibly related to TMZ
- Any TEAE leading to discontinuation of RT, possibly related to RT

- Any TEAE leading to dose-reduction of any study drug
- Any TEAE leading to dose-interruption of any study drug
- Any TEAE leading to death
- Deaths

This overview output will also be generated for each AESI, separately.

Adverse Events by System Organ Class and Preferred Term

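### The adverse-event and treatment-emergent windows close 49 days after the last ABT-414/placebo dose, while patients who stop that drug for toxicity continue protocol temozolomide

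*Protocol*

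**What the plan says.** **Collection.** Protocol Section 7.4 sets the main collection period: "From first day of component therapy administration until 49 days after last administered dose of ABT-414". Read with the SAP and the 49-day visit, ABT-414 here means ABT-414 or placebo.

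**Analysis.** SAP Section 7.3 limits treatment-emergent observations to onset "no later than 49 days after the last dose of Depatux-M/Placebo". SAP Section 11.2.1 defines a treatment-emergent AE (TEAE) as one starting or worsening "no more than 49 days after the last dose of Depatux-M/placebo". It also ends the adjuvant phase at that date, as does SAP Section 11.3. SAP Section 11.1 restricts most safety endpoints to treatment-emergent observations and reports incidence as simple frequencies and percentages.

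**Treatment after study drug stops.** Under Protocol Section 5.1, subjects who stop ABT-414/placebo for "toxicity prior to completion of the Adjuvant Therapy Phase will continue TMZ treatment as scheduled". Section 5.6 agrees: they "will be allowed to continue therapy with the other, tolerated therapy components until one of the other criteria above is met". The default schedule is in a Table 2 footnote: "TMZ will be administered once daily on Days 1 through 5 of each 28-day cycle for 6 cycles per the local prescribing information". Section 5.3.1.2 allows up to 12 cycles.

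**Scope of reporting.** Protocol Section 7.2 states: "Adverse event reporting is required for all protocol treatment modalities: ABT-414/placebo, TMZ, and radiation therapy". SAP Section 11.2.1 plans tables of TMZ-related AEs and of AEs leading to TMZ discontinuation.

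**Passages pointing the other way.** Protocol Table 2 schedules AE assessment on Day 1 of every adjuvant cycle, and only the Day 15 visit lapses once study drug stops. SAP Section 11.4.1 requires concurrent hepatic values to fall within 49 days of the last dose of any study drug.

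**The concern.** The windows follow one component of a three-component regimen. For a patient who drops ABT-414/placebo early and stays on TMZ, they close while protocol chemotherapy is still being given. Tables meant to describe TMZ toxicity and TMZ discontinuation then omit part of the TMZ exposure.

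The rule is the same in both arms, but its effect depends on who stops study drug early. The interim summary in Protocol Section 1.0 reports for corneal epitheliopathy: "11.8% and 0% discontinued study drug (ABT-414 or placebo) in the" ABT-414 and placebo arms respectively. If such stops come early, the ABT-414 arm's TMZ-period incidence is understated relative to placebo. Thrombocytopenia and neutropenia are events of special interest that the SAP itself expects from the disease or from RT/TMZ. Crude percentages would not reveal the shorter observation.

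**Working it through.** The plan states no figure for this point, so there is none to reproduce. The check is calendar arithmetic.

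**Inputs.** Study drug in chemoradiation is given on Days 1, 15 and 29 (Weeks 1, 3 and 5; Protocol 5.4). Adjuvant Cycle 1 starts about 28 days after the last radiotherapy day (Protocol 4.1). TMZ is given on Days 1–5 of 28-day cycles. The window closes at last ABT-414/placebo dose + 49 days. Assumption: radiotherapy ends on Day 42, so adjuvant day 1 is Day 42 + 28 = Day 70.

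**Step 1: TMZ cycles starting after closure.** Cycle c starts on adjuvant day 28(c − 1) + 1. Adjuvant day = study day − 69.

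| Last ABT-414/placebo dose | Adjuvant day | Window closes (+49) | Cycles starting later, 6-cycle plan | 12-cycle plan |
|---|---|---|---|---|
| Chemoradiation Week 5 | −40 | 9 | 5 of 6 | 11 of 12 |
| Cycle 1 Day 1 | 1 | 50 | 4 | 10 |
| Cycle 2 Day 1 | 29 | 78 | 3 | 9 |
| Cycle 3 Day 1 | 57 | 106 | 2 | 8 |
| Cycle 4 Day 1 | 85 | 134 | 1 | 7 |
| Cycle 4 Day 15 | 99 | 148 | 0 | 6 |
| Cycle 10 Day 1 | 253 | 302 | 0 | 1 |
| Cycle 10 Day 15 | 267 | 316 | 0 | 0 |

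The last TMZ dosing day is 28 × 5 + 5 = 145 in the 6-cycle plan and 28 × 11 + 5 = 313 in the 12-cycle plan. Stops at Cycle 4 Day 15 (window to day 148) and Cycle 10 Day 15 (to day 316) therefore lose no dosing day. This counts dosing days only: the Cycle 6 Day 22 blood count falls on day 140 + 22 = 162, beyond day 148.

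**Step 2: the Week 5 case.** Day 29 + 49 = Day 78, which is adjuvant day 9. Nine of 6 × 28 = 168 planned days, and 5 of 30 adjuvant TMZ dosing days, are inside the window.

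**Step 3: the SAP's adjuvant phase.** A last dose in Week 1 gives Day 1 + 49 = Day 50; in Week 3, Day 15 + 49 = Day 64. Adjuvant dosing, which SAP Section 7.4 counts from the first TMZ or study-drug dose, starts at about Day 70, or Day 68 if radiotherapy ends on Day 40. For these patients the adjuvant phase ends before it begins. Subjects given RT/TMZ but no ABT-414/placebo are in the safety set with no window end at all.

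**Step 4: possible size.** Taking about 320 treated per arm (assumed from 640 randomised 1:1), 0.118 × 320 ≈ 38 corneal stops against 0. Suppose all were early, and a share p of those patients had a first event of a given kind after closure. Arm A's crude incidence is then understated by 11.8 × p points:

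- p = 5%: 0.6
- p = 10%: 1.2
- p = 20%: 2.4
- p = 30%: 3.5

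These values of p are assumptions. For comparison, the interim summary selects events by differences of 2 points (Grade 3 or higher) and 5 points (any grade).

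**The case against.** The strongest reply is that the window suits the trial. TMZ is background standard of care in both arms, and 49 days after the randomised agent is used consistently in Protocol 7.4, the 49-day visit and the main SAP definitions. Study drug is planned for 12 cycles and TMZ by default for 6, so the window normally outlasts TMZ. A stop for progression ends adjuvant treatment altogether. Dose interruption and reduction come before many toxicity stops. Even the Week 5 patient has about 42 chemoradiation doses plus 5 adjuvant doses, 47 of 72 TMZ dosing days, inside the window. All of this stands, and it limits the point to a minority of patients. It does not explain how tables of TMZ-related AEs and TMZ discontinuations can omit TMZ cycles.

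Three stronger readings are tempting and are not supported:

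- *Late events are simply not collected.* Table 2 keeps AE assessment at every Day 1 visit. Section 4.2 requires an AE record for laboratory values that stop or interrupt TMZ, and Section 8.3.2 requires reasons for TMZ reduction or delay in the case report form. The passages conflict on collection; what is clear is exclusion from the TEAE tables.
- *Serious events on TMZ go unreported.* That depends on Section 7.5 and Figure 1, which are not in the text available for review, so no such claim is made.
- *The ABT-414 arm is observed for less time overall.* Total stops, their timing and treatment duration by arm are not given. Median PFS was longer on ABT-414 (8.0 versus 6.3 months), so the net difference cannot be signed.

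**Conclusion.** The point holds as a truncation of TMZ-period safety data in the analysis and a conflict over collection. Under the 6-cycle plan it costs between 1 and 5 whole TMZ cycles for a last study-drug dose between chemoradiation Week 5 and Cycle 4 Day 1, and no dosing days from Cycle 4 Day 15 onward. An earlier last dose leaves all adjuvant TMZ outside the window. If TMZ is extended to 12 cycles, the boundary moves to Cycle 10 Day 15.

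The difference in corneal stops shows that the truncation can fall more on the ABT-414 arm and understate its TMZ-period incidence. It does not show that it did, or by how much: the 0.6 to 3.5 point range rests on assumed timing and event shares. The day counts assume on-schedule treatment. The change is worth making because the SAP contradicts its own planned outputs and the remedy is cheap.

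**What to change.** 1. In SAP Sections 7.3, 11.2.1 and 11.3, end the treatment-emergent window and the adjuvant phase 49 days after the last dose of any protocol drug (ABT-414/placebo or TMZ), the kind of anchor SAP Section 11.4.1 already uses for concurrent hepatic values. No adjuvant TMZ cycle would then fall outside the window, whenever study drug stopped. Subjects who never received ABT-414/placebo would also have a defined end.
2. Keep the ABT-414/placebo-anchored window as a secondary summary, and add exposure-adjusted incidence rates by arm.
3. Reconcile Protocol Section 7.4 with Section 7.2 and Table 2, so that AEs at TMZ-only visits are explicitly collected.

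The cost is wording in both documents, some extra AE entry at visits already scheduled, and a second set of tables. For data already collected, the tables can be rerun with the wider window wherever later events were entered.
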